Documented evidence of IC at baseline is defined as having a radiologic test prior to the first dose of study drug that indicates new radiologic evidence of IC. Subjects who are diagnosed with IC by tissue/fluid culture whose first radiologic test is after the first dose of study drug are considered not to have a baseline radiologic test. In these subjects, radiology is not used to determine response.

Subjects who are diagnosed with candidemia at baseline (ie, prior to initiation of study drug) and progress to IC based on radiographic evidence or a tissue/fluid culture are considered to have IC for subsequent outcome assessments. The radiograph or tissue/fluid culture used to document progression is considered the baseline radiograph or tissue/fluid culture for outcome assessment.

The mycological eradication rate is the proportion of subjects with success (eradication/presumed eradication) out of the total number of subjects in the specified analysis population.

2.2.3. **Investigator's Assessment of Clinical Response**

The Investigator will make a determination of clinical cure at Day 5, Day 14 (± 1 day), Day 30 (-2 days), End of Treatment (≤ 2 days of last dose), and Follow Up (Days 52-59) according to the definitions in **Table 2-4**.

Subjects whose disease is progressing or who receive rescue antifungal therapy for candidemia/IC prior to an assessment time point will be considered a clinical failure at the assessment time point and all subsequent time points. Subjects who do not have resolution of systemic signs and symptoms but are improving at the day of assessment are considered a clinical failure. As long as no rescue antifungal therapy for candidemia/IC was received, the subject may still qualify as a cure at future visits as long as they meet the criteria of clinical cure at those visits. For example, at Day 14 (± 1 day) and Day 30 (-2 days), a subject who is on study drug can be a clinical cure if no rescue antifungal therapy for candidemia/IC was received and the subject meets the criteria of clinical cure even if they were assessed as a clinical failure at the Day 5 visit.

Table 2-4: Investigator’s Assessment of Clinical Response Definitions

Clinical Response	Definition

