2.8. Subgroup analyses

Subgroup analyses will be conducted for the FDA and EMA primary efficacy endpoints. The purpose of the subgroup analyses is to assess the consistency of treatment effect across potential or expected prognostic factors. Additional subgroup analyses may be also be conducted.

The list of subgroups will be finalized prior to database lock but will include:

- Sex (male versus female)
- Race (white versus non-white and Asian versus non-Asian)
- Age category (< 65 years versus ≥ 65 years)
- Geographic region (United States/South America, Europe/Israel/Turkey, Asia-Pacific (excluding China/Taiwan), China/Taiwan)
- Diagnosis at randomization (candidemia only versus IC)

- Final Diagnosis (candidemia only versus IC: progression from candidemia only to IC will be determined based on the radiological and/or tissue/fluid culture assessment through Day 14)
- APACHE II score/ANC at Screening (APACHE II score ≥ 20 OR ANC < 500 cells/ μ L versus APACHE II score < 20 AND ANC ≥ 500 cells/ μ L)
- APACHE II score at Screening (≥ 20 , < 20 , 10-19, < 10)
- ANC at Screening (< 500 cells/ μ L versus ≥ 500 cells/ μ L)
- Timing of culture used to document the *Candida* infection:
 - Positive culture at randomization definition 1: Subjects with a culture from blood drawn within 12 hours prior to randomization or within 72 hours after randomization, OR a culture from another normally sterile site obtained within 48 hours prior to randomization or within 72 hours after randomization; and
 - Positive culture at randomization definition 2: Subjects with a culture from blood drawn within 12 hours prior to randomization or within 72 hours after randomization, OR a culture from another normally sterile site obtained within 96 hours prior to randomization or within 72 hours after randomization

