4.3.1. Primary Efficacy Analysis

The analysis of the **primary efficacy outcome for the FDA** will be based on the mITT population.

The non-inferiority test will be a one-sided hypothesis test performed at the 2.5% level of significance. This non-inferiority test will be based on the upper limit of the two-sided 95% confidence interval (CI). The primary efficacy outcome is the percentage of subjects that died at Day 30.

The number and percentage of subjects in each treatment group that are alive and deceased (or with missing data) at Day 30 (-2 days) will be tabulated.

The null and alternative hypotheses are as follows:

$$H_0: p_1 - p_2 \geq \Delta, \text{ and}$$

$$H_1: p_1 - p_2 < \Delta,$$

where p_1 is the all-cause mortality rate at Day 30 (-2 days) in the Rezafungin for Injection treatment group, p_2 is the primary ACM at Day 30 (-2 days) rate in the caspofungin treatment group, and Δ is the non-inferiority margin of 20%.

To test the null hypothesis, a two-sided 95% CI for the observed difference in primary outcome rates (Rezafungin for Injection treatment group minus caspofungin treatment group) will be calculated for the mITT population using the unadjusted methodology of Miettinen and Nurminen (Miettinen and Nurminen, 1985). If the upper limit of the 95% CI for the difference in the mITT population is lower than 20%, then the null hypothesis will be rejected and non-inferiority of Rezafungin for Injection versus caspofungin will be declared.

To control the overall alpha level, superiority of rezafungin for ACM at Day 30 will be tested in the following order:

- If NI is declared for ACM at Day 30 in the mITT population and the rate of ACM at Day 30 in the rezafungin treatment group is lower than the caspofungin treatment group, the

difference between the treatment groups will be tested for superiority. If the upper bound of the 95% CI is less than 0, superiority of rezafungin will be concluded.

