- For the subgroup of subjects with invasive candidiasis (final diagnosis), a two-sided 95% CI for the observed difference in the rate of ACM at Day 30 will be calculated using the unadjusted methodology of Miettinen and Nurminen. If superiority is declared in the mITT population for ACM at Day 30 and the rate of ACM at Day 30 in the rezafungin treatment group is lower than the caspofungin group for invasive candidiasis subjects, superiority of rezafungin will be tested. If the upper bound of the 95% CI is less than 0, superiority of rezafungin will be concluded.

The analysis of the **primary efficacy outcome for the EMA** will be based on the mITT population. The non-inferiority test will be a one-sided hypothesis test performed at the 2.5% level of significance. This non-inferiority test will be based on the lower limit of the two-sided 95% confidence interval (CI). The primary efficacy outcome is the percentage of subjects that have a global response of cure at Day 14 (± 1 day) as confirmed by the DRC.

The number and percentage of subjects in each treatment group defined as global cure, failure and indeterminate will be tabulated, as will the overall category combining Failure and Indeterminate.

The null and alternative hypotheses are as follows:

$$H_0: p_1 - p_2 \leq -\Delta, \text{ and}$$

$$H_1: p_1 - p_2 > -\Delta,$$

where p_1 is the primary efficacy outcome rate in the Rezafungin for Injection treatment group, p_2 is the primary efficacy outcome rate in the caspofungin treatment group, and Δ is the non-inferiority margin of 20%.

To test the null hypothesis, a two-sided 95% CI for the observed difference in primary outcome rates (Rezafungin for Injection treatment group minus caspofungin treatment group) will be calculated for the mITT population. If the lower limit of the 95% CI for the difference in the mITT population exceeds -20% , then the null hypothesis will be rejected and the non-inferiority of Rezafungin for Injection to caspofungin will be declared.

To control the overall alpha level, superiority of rezafungin for global response will be tested in the following order:

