- If NI is declared and the percentage of subjects that have a global response of cure at Day 14 (± 1 day) as confirmed by the DRC in the rezafungin treatment group is higher than the caspofungin treatment group, the difference between the treatment groups will be tested for superiority. If the lower bound of the 95% CI is greater than 0, superiority of rezafungin will be concluded.

- For the subgroup of subjects with invasive candidiasis (final diagnosis), a two-sided 95% CI for the observed difference in global cure at Day 14 for the mITT population will be calculated using the unadjusted methodology of Miettinen and Nurminen. If superiority is declared for the EMA primary efficacy outcome of global response at Day 14 in the mITT population, and the global cure rate in the rezafungin treatment group is higher than the caspofungin group for invasive candidiasis subjects, superiority of rezafungin will be tested. If the lower bound of the 95% CI is greater than 0, superiority of rezafungin will be concluded.

A stratified 95% CI will be determined based on the two randomization strata: diagnosis (candidemia only; invasive candidiasis) and APACHE II score/ANC (APACHE II score ≥ 20 OR ANC < 500 cells/ μ L; APACHE II score < 20 AND ANC ≥ 500 cells/ μ L) at Screening. If there are < 5 subjects within a stratum and treatment group, or there is a 0 count within a stratum for a treatment group the categories will be combined. The 95% CI interval will be computed using the stratified methodology of Miettinen and Nurminen. Cochran-Mantel-Haenszel weights will be used for the stratum weights in the calculation of the CI as follows, where n_{1i} = number of subjects in Rezafungin for Injection treatment group in the i th stratum; n_{2i} = number of subjects in caspofungin treatment in the i th stratum:

$$W_i = \frac{n_{1i}n_{2i}}{n_{1i} + n_{2i}}$$

The reasons for having a global response of failure or indeterminate at Day 14 (± 1 day) will be presented using the number and percentage of subjects displayed by treatment group in the mITT population. Subjects who miss the efficacy assessment due to COVID-19 will have an indeterminate response and the number and percentage of subjects with an indeterminate response due to COVID-19 will be summarized.

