4.3.3. Subgroup Analyses of the Primary Outcomes

Subgroup analyses of mortality through 30 days (-2 days) and global response at Day 14 (± 1 day) will be performed to investigate the consistency of the treatment effects for different groups of subjects. Forest plots will be presented to visually assess the presence of treatment by subgroup interactions. All-cause mortality and global response at Day 14 (± 1 day) will be assessed separately within the following subgroups in the mITT population: sex (male versus

female), race (white versus non-white and Asian versus non-Asian), age category (<65 years versus ≥ 65 years), geographic region (United States/South America, Europe/Israel/Turkey, Asia-Pacific (excluding China/Taiwan), China/Taiwan), final diagnosis (candidemia only versus IC), and APACHE II score/ANC at Screening (APACHE II score ≥ 20 OR ANC < 500 cells/ μL versus APACHE II score < 20 AND ANC ≥ 500 cells/ μL), APACHE II score at Screening (≥ 20 , < 20, 10-19, < 10), ANC at Screening (< 500 cells/ μL versus ≥ 500 cells/ μL). All-cause mortality through 30 days (-2 days) and global response at Day 14 (± 1 day) will also be summarized in the subgroups defined by timing of the culture used to document the *Candida* infection (positive culture at randomization definitions 1 and 2). This subgroup will not be included in the Forest plots.

For each subgroup, the number and percentage of subjects alive and deceased at Day 30 and the number and percentage of subjects with a global cure, failure and indeterminate response at Day 14 (± 1 day) will be determined by treatment group. Two-sided 95% CIs for the observed difference in mortality rates and global cure rates will be calculated in the mITT population, using the unadjusted methodology of Miettinen and Nurminen.

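### The final superiority test in invasive candidiasis, inside the alpha-controlled sequence, uses a subgroup fixed after randomization that treatment can change

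*SAP*

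**What the plan says.** SAP 4.3.1 sets an ordered sequence for each primary outcome: non-inferiority, then superiority in the mITT population, then superiority in IC. For mortality it is introduced with "To control the overall alpha level, superiority of rezafungin for ACM at Day 30 will be tested in the following order", and the global cure sequence has a matching introduction. The last mortality step reads "For the subgroup of subjects with invasive candidiasis (final diagnosis), a two-sided 95% CI for the observed difference in the rate of ACM"; the last cure step reads "For the subgroup of subjects with invasive candidiasis (final diagnosis), a two-sided 95% CI for the observed difference in global cure at Day 14".

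SAP 2.8 explains final diagnosis: "progression from candidemia only to IC will be determined based on the radiological and/or tissue/fluid culture assessment through Day 14". The same list has diagnosis at randomization as a separate subgroup. SAP 4.3.3, which specifies the subgroup analyses and forest plots, lists only final diagnosis.

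Protocol 13.4.1.1 and 13.4.2 describe the same two steps for subjects with IC, with no mention of final diagnosis. The diagnosis grouping those sections name is the randomization stratification factor. SAP section 6 states that nothing differs from the protocol.

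SAP 3.5 says no multiplicity adjustment is used. I take the ordered sequence in 4.3.1 as the intended rule, but the two sections should be reconciled.

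**The concern.** A subgroup test keeps the protection of randomization only if membership is fixed before treatment can act. Here a candidemia-only subject joins the IC subgroup if imaging or a tissue/fluid culture shows IC by Day 14. Protocol 7.4.2 itself ties spread after enrollment to a possible lack of drug effect.

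For global cure the grouping also overlaps the outcome. SAP 2.2.3 says "Subjects whose disease is progressing or who receive rescue antifungal therapy for candidemia/IC prior to an assessment time point will be considered a clinical failure", and clinical failure makes global response a failure (SAP Table 2-2). SAP 2.2.2 softens this for imaging and culture: "The radiograph or tissue/fluid culture used to document progression is considered the baseline radiograph or tissue/fluid culture for outcome assessment". That resets the reference test but does not restore a randomized comparison. For mortality, a candidemia subject who dies before any such test cannot be reclassified.

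If progression differs by arm, the arm with more of it has its progressors, probably with poor outcomes, added to its own IC group. A confirmatory claim in IC could then rest only on fewer candidemia patients progressing. If progression is commoner on rezafungin, the distortion runs the other way.

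**Working it through.** **Plan figure used as an input.** The 92 per arm reproduces. For cure of 70%, margin 20% and one-sided 2.5%, the uncorrected size is 82.4 per arm, and the continuity correction gives 82.4/4 × (1 + √(1 + 4/(82.4 × 0.2)))² = 92.1. Power for mortality at 92 per arm is 89.4%, against 89.7% stated. The concern does not depend on these figures.

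**Inputs.**
- From the documents: 92 per arm (protocol 13.8), and 20.8% IC at entry (the Phase 2 figure, protocol 4.7.2). This gives 92 × 0.208 = 19.1 IC and 72.9 candidemia-only subjects per arm.
- Assumed, because the documents give no values: no treatment effect in IC present at entry (cure 60% in both arms), cure in progressors 10%, and the progression rates in the table.

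**Expected cure rate in IC by final diagnosis**, with progression p: (19.1 × 0.60 + 72.9 × p × 0.10) / (19.1 + 72.9 × p).
- 4%: 11.77/22.05 = 53.4%. 10%: 12.21/26.42 = 46.2%. Difference +7 points.
- 2%: 11.63/20.59 = 56.5%, against 46.2%. Difference +10 points.
- 5%: 11.85/22.78 = 52.0%. 15%: 12.57/30.07 = 41.8%. Difference +10 points.

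By diagnosis at randomization the difference is 0 in each case.

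**Rejection rates**, from 200,000 simulated trials per scenario. The Miettinen-Nurminen score test at zero, one-sided 2.5%, was used for both the mITT gate and the IC step. It was unstratified throughout, which simplifies the stratified interval planned for cure.

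| Progression, rezafungin v caspofungin | IC step alone | Gated, non-progressor cure 75% v 75% | Gated, non-progressor cure 92% v 70% |
|---|---|---|---|
| 4% v 10% | 7.1% | 2.1% | 7.1% |
| 2% v 10% | 10.1% | 3.1% | 10.1% |
| 5% v 15% | 10.8% | 4.1% | 10.9% |
| 5% v 5% | 2.5% | 0.5% | 2.5% |
| 10% v 4% | 0.7% | 0.1% | 0.7% |

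By diagnosis at randomization, the step alone rejects 2.4-2.5% throughout. For the first three rows its gated rates are 0.8-1.1% (75% v 75%) and 2.4-2.5% (92% v 70%). In those rows the mITT gate opens in 6-11% of trials when non-progressor cure is equal, and in 86-90% when it is 92% v 70%.

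**Sensitivity.** With progressor cure of 30%, the step alone rejects 4.7%, 6.0% and 6.4% for the first three rows, and the gated rates at 75% v 75% are 1.3%, 1.7% and 2.1%. A milder 5% v 8% progression (progressor cure 10%) gives 1.1% gated.

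**Mortality.** Assumptions: 20% in IC at entry, 40% in progressors, progression 5% v 10%, 15% and 20%. The step alone rejects 3.6%, 4.8% and 6.1%, against 2.4% by diagnosis at randomization. Gated, the rates are 0.8%, 1.2% and 1.8% with non-progressor mortality of 20% in both arms, and 3.6%, 4.9% and 6.0% with 5% v 25%.

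**The case against.** - **Analyses by baseline diagnosis are already planned.** Protocol 13.4.1.1 and 13.4.2 require both primary outcomes by the stratification factors, with confidence intervals, and SAP 2.8 lists diagnosis at randomization. A reader would therefore see a baseline-IC estimate beside the tested one. This stands, but those analyses are descriptive and do not change the group in which the claim is tested.
- **The protocol never defines IC in this step,** so final diagnosis may fill a gap rather than depart from the protocol. That is arguable. The choice still adds a post-randomization definition that section 6 does not mention.
- **There is no inflation when treatment does not affect progression.** Every inflated scenario assumes that rezafungin prevents progression, which is a real benefit. This is correct: the claim is false only as a statement about patients who had IC at entry. That is how a claim of superiority in IC would be read.
- **The largest figures need generous inputs.** Candidemia cure of 92% v 70% implies about 83% v 63% overall (4% v 10% progression), against the planned 70% v 70%. With neutral inputs, several gated rates stay below 2.5%. This limits the size of the concern. At the Phase 2 overall success rates (76.1% v 67.2%), however, the gated rate is 4.9-7.1% with progressor cure of 10%, or 3.5-4.6% with 30%.
- **Late detection.** Screening imaging is recorded only if performed (protocol 9.1), and protocol 7.4.2 recognises IC present at entry but diagnosed late. Final diagnosis captures these subjects and diagnosis at randomization does not. This is a genuine cost of the fix.

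**Conclusion.** The concern holds and should be fixed. The text is clear: a confirmatory subgroup is defined by events up to Day 14 that treatment can influence, and for cure those events overlap the outcome. The size is uncertain because progression rates and progressor outcomes are assumed. In the cure scenarios with less progression on rezafungin and progressor cure of 10%, the gated false-claim rate for IC at entry runs from 1.1% to 10.9%. It is highest when rezafungin is truly better in candidemia, because the gate then gives almost no protection. With equal progression nothing is lost.

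The reach is limited. Both non-inferiority conclusions and mITT superiority are untouched, and the step is taken only after both have been shown.

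**What to change.** In both superiority sequences of SAP 4.3.1, define the IC subgroup by diagnosis at randomization. Add that subgroup to the list and forest plots in SAP 4.3.3 so that they match SAP 2.8. Keep final diagnosis as a descriptive summary, labelled as a post-randomization grouping outside the testing sequence. If the sponsor keeps it in the plan for another purpose, section 6 should record and justify it.

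The change needs an SAP amendment before database lock, which SAP 1.1.1 allows, and one program change to a variable already held for stratification. There are two costs. The IC test shrinks to about 19 per arm, from about 21-30 under the assumptions above. IC present at entry but found late no longer counts as IC in the test, although the descriptive summary still shows those subjects.

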4.3.1.1. Additional Analyses of the Primary Efficacy Outcomes

Sensitivity analyses of the primary outcome for FDA include:

- The first sensitivity analysis will exclude subjects whose survival status is not known (these subjects are considered deaths in the primary analysis).
- The second sensitivity analysis will calculate an adjusted (for the randomization stratification factors) 95% CI interval using the stratified methodology of Miettinen and Nurminen. As noted above, Cochran Mantel Haenszel weights will be used for the stratum weights in the calculation of the CI.
- The third sensitivity analysis will be conducted using multiple imputation for missing data. Missing primary outcome data will be imputed with multiple imputation. Fifty data sets will be created by treatment group using a logistic regression in which the randomization stratification factors of diagnosis (candidemia only; invasive candidiasis)

and APACHE II score/ ANC (APACHE II score ≥ 20 OR ANC < 500 cells/ μ L; APACHE II score < 20 AND ANC ≥ 500 cells/ μ L) at Screening are included as predictive variables. The seed number of 101305 will be used. The difference in mortality rate is calculated per each imputed dataset and the risk differences are combined using proc mianalyze.

Sensitivity analyses of the primary outcome for EMA include:

- The first sensitivity analysis will consider indeterminate responses as successes.
- The second sensitivity analysis will present an unadjusted two-sided 95% CI for the observed difference in primary outcome rates (Rezafungin for Injection treatment group minus caspofungin treatment group) using the methodology of Miettinen and Nurminen.
- The third sensitivity analysis will analyze the primary outcome for the EMA in the CE population. The number and percentage of subjects with a global response of cure and failure will be provided along with an adjusted (for the randomization stratification factors) two-sided 95% CI for the difference in global cure rates.

4.3.2. Secondary Efficacy Outcomes

The secondary efficacy endpoints of clinical response as assessed by Investigator, mycological response (programmatically derived), radiological response (for subjects with invasive candidiasis documented by radiologic/imaging evidence at baseline) will be presented using the number and percentage of subjects with a response of cure (eradication for mycological response), failure, or indeterminate, displayed by treatment group in the mITT population at Day 5, Day 14 (± 1 day), Day 30 (-2 days), End of Treatment (≤ 2 days of last dose), and Follow-up (Days 52-59).

The number and percentage of subjects with a global response of cure, failure, or indeterminate (confirmed by the DRC) will be presented by treatment group in the mITT population at Day 5, Day 30 (-2 days), EOT (≤ 2 days of last dose) and Follow-up (Days 52-59). 95% CIs for the treatment differences in global cure will be determined.

Treatment differences in secondary efficacy endpoints will be assessed using 95% CIs calculated at Day 5, Day 14 (± 1 day), Day 30 (-2 days), End of Treatment (≤ 2 days of last dose), and Follow-up (Days 52-59). Two-sided 95% CIs will be constructed for the observed differences in the global cure, mycological eradication, radiologic cure and clinical cure rates using the method of Miettinen and Nurminen without stratification. The 95% CIs are for descriptive purposes only.

Analyses by diagnosis (candidemia only; invasive candidiasis) and APACHE II score/ ANC (APACHE II score ≥ 20 OR ANC < 500 cells/ μ L; APACHE II score < 20 AND ANC ≥ 500 cells/ μ L) at Screening will also be provided.

